5.3 Sample

The study will have three groups of participants:

- A. Intervention group - people using the mental health services of the partner organisation at the case study sites (n=40) who will participate in the walking groups,
- B. Non-walking group - people using the mental health service of the partner organisation who choose not to participate in the walking groups, but consent to be involved in the research (n=40), and
- C. NWG facilitators - employees of the partner organisations responsible for service delivery at the case study sites (n=10).

Forty participants will be recruited at each site (ICMHS and LikeMind) (n=80) from the mental health consumers receiving services. Approximately 100 consumers receive services at these agencies at any given time.

5.3.1 Group A - Eligibility criteria

The inclusion criteria for joining the NWG are following:

- Currently receives mental health services at ICMHS or LikeMind
- Shows interest and commitment to be part of a 12-week program of weekly nature walking groups
- Completed and passed the health moves assessment (see Appendix 12.7)
- Ability to walk unassisted for up to 60 minutes at low intensity (see the Grading System in Section 10.5)

The exclusion criteria:

- Cannot participate in at least 10 of the 12 scheduled NWGs
- Instability in current mental health, for example, a current intent or plan of suicide

5.3.2 Group B – Eligibility criteria

The inclusion criteria for the non-walking group include the following:

- Currently receives mental health services at ICMHS or LikeMind
- Is not interested in participating in the nature walking groups, or have not passed the health moves assessment and/or has been assessed by their primary physician as incapable of participating in the NWG's.

The exclusion criteria:

- Instability in current mental health, for example, a current intent or plan of suicide

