5.4 Recruitment (Groups A and B)

The research team will attend a facilitator training to introduce the project and explain the research steps and processes. Recruitment flyers will be distributed at each of the study sites (See Appendix 12.1). Each location will have a study co-ordinator (TC, LikeMind, and PD, ICMHS) who hold managerial positions in each study site. The study site co-ordinator at each site will provide treating clinicians with an overview of the study and NWGs. Clinicians can then discuss participation with existing clients on their caseload and provide them with information on the study and the contact details of the research team. Some treating clinicians will also be trained NWG facilitators, however, they will not enrol potential participants into the study, or gain consent. Once all potential participants have been connected with the research team to express their interest, an information day will be conducted by research team members at each site. People who cannot attend the information session will be followed up by the research team.

Potential participants will receive a Participant Information Sheet (see Appendix 12.3) where they can learn more about the research project. Specifically, that participation in the NWG will involve:

- completing an online or pen and paper survey at the commencement and conclusion of the 12-week session,
- completing a brief mood question, pre- and post- each walk,
- participating in a walk once a week for 12 weeks at a location they will be transported to,
- participating in a 2 hour closing focus group at the 12th walk,
- completing one phone interview with a member of the research team, and
- providing 3 saliva samples for cortisol and DHEA testing one week before commencement, at the end of the first walk and conclusion of the last walk but that this will be **optional**.

If people consent to be part of the research, they will be invited to join the first walk. If they do not wish to join the NWG, or if they are not eligible to participate due to the results of the screening assessment (See Appendix 12.7), they will be allocated to Group B and provided a Participant Information Sheet (Appendix 12.4) which will include all details relating to the measures included in the survey to be completed at the beginning and end of a 12 week period, and the optional collection of a saliva sample for cortisol and DHEA testing at the same time as completing the survey.

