7 DATA ANALYSIS

A frequentist statistical approach will be adopted for quantitative data analysis, using SPSS or R software. Specifically, analysis of variance will provide objective evidence of the efficacy of the NWG intervention.

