10 ETHICAL CONSIDERATIONS

10.1 Recruitment and Selection of Participants

Participants will be recruited through the existing caseloads of ICMHS and LikeMind, offering participation to any interested person, capping the number at ten for each NWG. Participants in the research will continue receiving the usual one-on-one support throughout the duration of the research. Participants will be recruited in March-April 2024, with the aim of beginning the NWG sessions at the end of April 2024 and concluding the first group in July 2024. The second group will commence in each site in approximately September, concluding in November. Start and finish dates may vary in each site depending on numbers of participants recruited and weather (too hot or cold). Consumers will be informed about the project by staff of the services. If they express an interest in participating, they will be provided with an information sheet and invited to a NWG information session facilitated by the research team. Consumers who are not interested in participating in the walking groups will also be invited to the study to be part of Group B. Consumers who are interested in participating in Group B will be invited to an information session facilitated by the research team where the study and data collection requirements will be explained, information sheets will be provided and consent to participate sought from volunteers. Potential participants who are unable to attend the information day will have a time organised to meet individually with one of the research team at the study site or via a phone call.

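### Interest and fitness decide who is in Group A or Group B, so the A-versus-B difference is confounded by selection and cannot be called objective evidence of efficacy

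*Protocol*

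**What the plan says.** Section 5.3.1 admits a person to Group A who "Shows interest and commitment to be part of a 12-week program of weekly nature walking groups", who has "Completed and passed the health moves assessment" and who can walk unassisted for up to 60 minutes. It excludes anyone who "Cannot participate in at least 10 of the 12 scheduled NWGs".

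Section 5.3.2 sets the Group B criterion: "Is not interested in participating in the nature walking groups, or have not passed the health moves assessment", and/or a person who "has been assessed by their primary physician as incapable of participating in the NWG's". Section 5.4 allocates in the same way, sending people to Group B "If they do not wish to join the NWG, or if they are not eligible to participate due to the results of the screening assessment". Section 5.3 is narrower and describes Group B only as people who choose not to walk. Section 10.1 offers walking places to any interested person, "capping the number at ten for each NWG".

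The Study Summary calls Group B the control. Section 7 states that "analysis of variance will provide objective evidence of the efficacy of the NWG intervention". Section 7.1 powers the difference between the groups at follow-up, assumes the same baseline mean in both, and says the sample allows the program's effectiveness to be assessed.

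**The concern.** Willingness to join a 12-week walking program and physical fitness to do so are traits that plausibly bear on the course of depression and anxiety, whatever the walks do. Here they are the rule of entry to each group, so the imbalance is systematic. A larger sample would estimate the confounded difference more precisely without making it less confounded.

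The eligibility rules also leave a gap. A person who is interested and fit but cannot attend 10 walks is excluded from Group A and meets no criterion in Section 5.3.2. So does any interested, fit person left without a place once both rounds are full. Such people resemble Group A on the two traits that separate the groups.

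At stake is the reading of the primary result. A significant A-versus-B difference would be reported under a sentence that already calls it evidence of efficacy, and the design cannot support that.

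**Working it through.** **1. Who can enter which group.** People with current mental-health instability are excluded from both groups and are left out here. Fit means having passed the screen and not having been judged incapable by a physician.

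| Person | Group A (5.3.1) | Group B (5.3.2) |
|---|---|---|
| Interested, fit, can attend 10 or more walks, place free | yes | no |
| Interested, fit, cannot attend 10 walks | excluded | meets no criterion |
| Interested, fit, over the cap after both rounds | no place | meets no criterion |
| Interested, failed the screen or judged incapable | no | yes |
| Not interested (may never have been screened) | no | yes |

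Everyone in Group A is interested and fit. No one who meets the Group B criteria is both. The groups do not overlap on that combination, so covariate adjustment can reduce the confounding but not remove it.

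**2. The protocol's sample size.** The inputs are from Section 7.1: baseline mean 22.76 (SD 9.46), intervention follow-up mean 16.08 (SD 10.41), 80% power and 5% significance (two-sided assumed).

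- Difference: 22.76 − 16.08 = 6.68.
- Normal approximation: n per group = (1.960 + 0.842)² × (9.46² + 10.41²) / 6.68² = 34.8, so 35.
- Two-sample t-test with SD = √((9.46² + 10.41²)/2) = 9.946: power is 79.1% at 35 and 80.2% at 36 per group.
- Total: 2 × 36 = 72, and 72 / 0.90 = 80.

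The stated 72 and 80 are reproduced. The arithmetic is sound. The difficulty is that the calculation attributes the whole 6.68 points to the intervention and takes the groups as equal at baseline.

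**3. What a selection-only gap would do (illustration).** The protocol gives no size for the gap, so the values of b below are assumptions. With no true effect, 36 per group and a follow-up comparison without baseline adjustment:

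- Standard error = 9.946 × √(2/36) = 2.344.
- Noncentrality = b / 2.344, with critical t on 70 df = 1.994.

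| Assumed gap b (points) | In baseline SDs (b / 9.46) | Noncentrality | Chance of p<0.05 |
|---|---|---|---|
| 0 | 0 | 0 | 5% |
| 1 | 0.11 | 0.43 | 7% |
| 2 | 0.21 | 0.85 | 13% |
| 3 | 0.32 | 1.28 | 24% |
| 4 | 0.42 | 1.71 | 39% |

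More participants would shrink the standard error and raise these percentages.

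**4. Power if screen failures are left out of Group B.** With 36 in Group A, n in Group B, a difference of 6.68 and SD 9.946, the standard error is 9.946 × √(1/36 + 1/n). The numbers in Group B are assumed.

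- n = 27: standard error 2.53, power about 74%.
- n = 18: standard error 2.87, power about 63%.
- n = 12: standard error 3.32, power about 50%.

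**The case against.** The best defence is that this is a pilot and says so. Section 7.1 calls it a pilot feasibility trial, the study is a mixed-methods RE-AIM evaluation, and Section 5.3 states openly that Group B members choose not to walk. A non-randomised comparator is a legitimate choice in that setting. That stands as a defence of the design. It does not rescue the efficacy sentence in Section 7 or the effectiveness sentence in Section 7.1, which the pilot label leaves in place.

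Several stronger readings are tempting and should not be drawn:

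- **That the groups differ by rule in mental-health stability.** They do not. Sections 5.3.1 and 5.3.2 carry the same exclusion.
- **That the planned analysis is unadjusted.** Section 7 says only analysis of variance. Covariates may be set in an analysis plan that is not shown, so their absence here is not a fault.
- **That the bias must favour the walking groups.** The protocol has no data on distress by interest or fitness. If less fit Group B members start with higher scores, regression to the mean could favour Group B on change scores.
- **That people over the cap are turned away.** Each site runs two groups of ten (Section 9), the second from about September (Section 10.1). Someone over the cap in the first round may join the second. The cap excludes people only if more than 20 eligible people at a site want to walk, and no such number is given.
- **That the percentages above estimate this trial's error rate.** They apply to the follow-up comparison on which the sample size rests. Section 7.1 also names a Wilcoxon signed ranks test on change. A stable baseline gap would cancel in change scores, and only a difference in course would bias them.

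A person unable to attend 10 walks might also be read into the looser wording of Section 5.3. That makes part of the gap an inconsistency between sections.

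**Conclusion.** The point holds in this form. Sections 5.3.1, 5.3.2 and 5.4 assign people by interest and fitness, so the A-versus-B difference is confounded by selection, in a direction the protocol does not establish. It cannot be objective evidence of efficacy, nor can it show the program's effectiveness without qualification.

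The size of the bias is unknown. Under assumed gaps of 1 to 4 points, the false-positive rate of a follow-up comparison without baseline adjustment would rise from 5% to between about 7% and 39%. This rests on the protocol's SDs, 36 per group, a two-sided t-test and no true effect. That interest and fitness relate to the course of distress is reasoned inference and not a figure in the document. The number of interested, fit people left outside both groups is not stated.

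**What to change.** 1. Reword Sections 7 and 7.1 so that the result is described as a preliminary, non-randomised estimate of the difference between walkers and non-walkers.
2. Estimate that difference adjusted for baseline PHQ-ADS and site, both already collected, and state that this reduces but does not remove confounding.
3. Record the reason for each Group B entry: declined, cannot attend, over the cap, or failed the screen or physician check. As a sensitivity analysis, compare Group A with Group B after leaving out those who failed the screen or physician check. Say that its power is lower (about 74%, 63% or 50% with 27, 18 or 12 left in Group B) and that decliners may never have been screened. For those reasons it should not be the primary contrast.
4. Reconcile Sections 5.3, 5.3.2 and 5.4 on who may join Group B. If recruitment still allows, let interested people who cannot attend 10 walks, or who are over the cap, join Group B.

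The cost is a softer claim, one extra data item and some rewording. If eligibility can no longer change, items 1 to 3 and the reconciliation of the text remain possible.

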3 STUDY SUMMARY

Aims: This study aims to 1) evaluate the implementation of structured Nature Walking Groups (NWG) in mental health services, 2) identify the impact of facilitated nature contact for people living with severe and persistent mental health conditions, and 3) deliver evidence-based guidelines for service providers to implement and evaluate NWGs supporting future implementation and research.

Setting: Nature Walking Groups will be delivered in two sites in NSW – Orange (Non-Government Organisation) and Wollongong (Government led Mental Health Service).

Approach: The RE-AIM framework will be used to guide the collection of quantitative and qualitative data and their analysis.

Sample: Three groups of participants will be recruited; Group A – Intervention (n=40), Group B – non-walking group (n=40), and Group C – Nature Walking Group facilitators (n=10).

The intervention: A total of four NWGs over 12 months will be conducted in the two sites by the trained Nature Walking Group facilitators (Group C; n=10). Intervention participants (Group A; n=40) will participate in one NWG, receiving 1 hour per week in nature for a continuous period of 12 weeks (twelve walks per participant), while still also receiving treatment as usual (TAU). On each walk, facilitators will draw participant attention to one of the natural features and guide participants through stress reduction and mindfulness activities, lasting 3 to 10 minutes in duration. Individuals in Group B (control; n=40) will continue to receive TAU.

Data collection + procedures: Clinicians in both sites will be invited by site coordinators to undertake NWG facilitator training (Group C; n=10). Following training, facilitators will be invited to complete an Organisational Readiness Survey.

Information session will be held in each participating site, where researchers will recruit participants to either Group A (intervention) or Group B (non-walking). Participants in Group A and Group B will be invited to complete baseline surveys, and the first of three salivary samples to be collected at different intervals during the project for cortisol and Dehydroepiandrosterone (DHEA) testing (n=80).

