6.6 Pre, post and 3-month follow-up Surveys (Group A and B)

An online or pen and paper survey (See Appendix 12.6) will be completed by participants in groups A and B at baseline, 12 weeks post-baseline (post NWG) and at 3 post-intervention. The following scales will be included:

Table 4 - Pre, post and 3-month follow-up survey scales

Primary Outcome Measure	The Patient Health Questionnaire for Anxiety and Depression (PHQ-AD) (16 items)
Secondary Outcome Measures	Personal Wellbeing Index (7 items)
	Pittsburg Sleep Quality Index (2 items)
	DeJong Gierveld Loneliness Scale (6 items)
	Nature Relatedness Scale – short form (6 items)
	The Warwick Edinburgh Mental Well Being Scale (7 items)
	Major life event, positive or negative (2 items)
	Connor-Davidson Resilience Scale (2 items)

In addition, participants in the NWG will be asked to report their mood pre- and post-walking session, as described in Section 6.8.

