7.1 Sample size and power calculation

While sample size calculation is crucial for a pilot study, achieving adequate power through formal calculations can be challenging (Billingham et al., 2013). Nonetheless, we have derived the sample size for this study by considering the estimated effect size observed in the literature for various mental health indicators. According to the conceptual framework of the proposed pilot feasibility trial study, the primary outcome measure was the level of distress measured by Patient Health Questionnaire Anxiety and Depression Scale (PHQ-ADS). In a recent randomized controlled trial study in the UK conducted by Picariello et al. (2024), it was found that the mean level of distress among the study participants was 22.76 (SD, 9.46), which decreased by 30% immediately after the cognitive behavioural therapy intervention. We utilized these study findings to inform the parameters for the sample size calculations in our study. We assumed the mean level of distress will be about 22.76 (with SD, 9.46) among the study participants at baseline in both control and interventions group (Picariello et al., 2024). After the program implementation, the mean level of distress will be reduced to 16.08 (SD, 10.41) among the participants in interventions group (assuming about 30% reduction by the intervention; Picariello et al. (2024). To ensure a minimum detectable difference in the mean distress level between the intervention and control groups at follow-up, with a power of 80% and a 5% level of significance, a minimum sample size of 72 participants is required (36 participants in each group). Anticipating 10% loss to follow-up, we plan to include 80 participants in total. Therefore, data will be collected from at least 40 participants in both the control and intervention groups, enabling to assess the program's effectiveness in improving mental health outcomes. Our planned sample size falls within the range of suggested sample sizes for pilot and feasibility studies as per the guidelines, which recommend 30-59 participants (Billingham et al., 2013; Viechtbauer et al., 2015).

The outcomes will be analysed using a Wilcoxon signed ranks test to calculate change between scores because measures contain ordinal data and a test that does not assume a normal distribution is required. A W-statistic is appropriate for a small number of linked observations.

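### Control Group B mixes people who declined to walk with people medically barred from Group A; route of entry should be recorded, the A-versus-B analysis adjusted for baseline, and a by-choice sensitivity analysis reported

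*Protocol*

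**What the plan says.** All references are to the protocol.

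- **Group A (5.3.1).** Members must have passed the health moves assessment. They must also meet this criterion: "Shows interest and commitment to be part of a 12-week program of weekly nature walking groups".
- **Group B (5.3.2).** Besides people who are not interested in walking, it takes those who fail the screen or whom a doctor rules out: "or have not passed the health moves assessment and/or has been assessed by their primary physician as incapable of participating".
- **Allocation (5.4).** People who do not want to walk go to Group B, and so do others "if they are not eligible to participate due to the results of the screening assessment". The physician route is not mentioned here.
- **Summary definition (5.3).** Group B is service users "who choose not to participate in the walking groups, but consent to be involved in the research". Sections 10.1 and 10.3 likewise describe Group B by lack of interest.
- **Role of Group B (3).** "Individuals in Group B (control; n=40) will continue to receive TAU".
- **Sample size (7.1).** The study is sized for "a minimum detectable difference in the mean distress level between the intervention and control groups at follow-up", on PHQ-ADS, assuming the same baseline mean and SD in both groups.
- **Analysis.** Section 7 opens by naming analysis of variance for efficacy. Section 7.1 closes by assigning the outcomes to a Wilcoxon signed ranks test of change, and Table 1 names the same test for the surveys.
- **Baseline data (6.6).** The survey containing PHQ-ADS "will be completed by participants in groups A and B at baseline", and again at 12 weeks and at the 3-month follow-up.

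**The concern.** A failed health moves assessment bars a person from Group A and qualifies the same person for Group B. Screen failures can therefore appear only among the controls. (Section 5.3.1 has no physician criterion, so the strict non-overlap is claimed for screen failures only.) The groups are openly self-selected, so some imbalance is already accepted. The medical route adds a second difference, in fitness to walk, to the one comparison that section 7.1 powers.

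The protocol also disagrees with itself on who the controls are: decliners only in 5.3, 10.1 and 10.3, a mixture in 5.3.2 and 5.4. Sections 5.3.2, 5.4 and 6.6 do not ask for the route of entry to be noted. Without it, a reader cannot tell how many controls came by each route or whether the result depends on them.

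The analysis sentence compounds this. A signed-rank test is paired and describes change within a group. It does not by itself deliver the between-group comparison on which the sample size rests, nor does it use the baseline score to reduce imbalance between the groups.

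**Working it through.** **1. Reproduce the plan's figure.** Inputs from 7.1: means 22.76 and 16.08, SDs 9.46 and 10.41, power 80%, alpha 5%. Assumed, because not stated: a two-sided test and a control mean that stays at 22.76.

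- Difference = 22.76 − 16.08 = 6.68.
- SD = √[(9.46² + 10.41²)/2] = 9.95, so d = 6.68/9.95 = 0.672.
- Two-sample t power (noncentral t): 79.1% at 35 per group and 80.2% at 36.
- 36 × 2 = 72, and 72/0.90 = 80 enrolled.

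The stated 72 and 80 reproduce. The sample size is not in error.

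**2. What the mixture could do.** The protocol gives neither the share of medical entrants nor their PHQ-ADS gap, so these are assumptions: share f = 0.25, gap 0.25 to 0.5 of the baseline SD (2.4 to 4.7 points), in either direction.

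- Shift in the unadjusted follow-up difference = f × gap: 0.25 × 0.25 × 9.46 = 0.59 points, and 0.25 × 0.5 × 9.46 = 1.18 points.
- As a share of 6.68: 8.9% and 17.7%.
- If medical entrants score worse than decliners, the apparent effect is inflated.
- If they score better, the expected difference falls to 6.09 or 5.50 points, and power at 36 v 36 falls from 80% to 73% or 64%.

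**3. What baseline information removes.** A gap that is constant over time cancels in change scores. Baseline adjustment reduces it: with an assumed slope of 0.5, half remains, about 0.30 to 0.59 points. A different course over time is not removed by either method. If medical entrants change by 2 to 5 points more or less than decliners, the shift is 0.25 × 2 = 0.5 to 0.25 × 5 = 1.25 points.

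**4. Power with some of Group B set aside.** Group A is 36 evaluable. Baseline adjustment is represented by d/√(1 − r²), where r is the assumed correlation of baseline with follow-up.

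| Share of B set aside (assumed) | A v B | r = 0 | r = 0.3 | r = 0.5 |
|---|---|---|---|---|
| 0% | 36 v 36 | 80.2% | 83.8% | 90.1% |
| 10% | 36 v 32 | 77.8% | 81.5% | 88.2% |
| 25% | 36 v 27 | 73.8% | 77.7% | 85.0% |
| 50% | 36 v 18 | 62.7% | 66.8% | 75.1% |

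Using the two SDs separately instead of their average changes the unadjusted 25% row to 74.4% and the 50% row to 64.1%. At 36 v 27, a correlation of 0.38 is enough to return to the unadjusted 36 v 36 power.

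**5. Which controls resemble Group A?**

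| | Interest in walking | Fitness to walk |
|---|---|---|
| Group A | required | screen passed |
| B, by choice | lacking | not known; no text says decliners are screened |
| B, failed screen | plausibly present, since they took the assessment | screen failed |

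Each subset differs from Group A on a different factor.

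**The case against.** A reader might infer that the main comparison should be confined to decliners. The documents do not support that. Sections 5.3.1 and 5.4 suggest that those who took the assessment are largely people who wanted to walk, so dropping them removes the controls most likely to share Group A's interest. Nothing says decliners are screened, so people who would have failed stay in the supposedly cleaner group. The bias has unknown direction, whereas the loss of power is certain. This objection stands, and it is why the restriction belongs in a sensitivity analysis.

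A reader might also infer that medical entrants could never be separated later. That goes too far. Allocation follows an assessment result, so screen failures should have one, and the screening form (Appendix 12.7) and survey (Appendix 12.6) are not shown. What can be said is that the visible text does not ask for the route to be recorded. The gap is plainest for the physician route.

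A further objection is that analysis sets, covariates and sensitivity analyses are commonly left to a statistical analysis plan, that this is a self-described pilot feasibility trial with openly non-randomised groups, and that the 9% to 18% shift applies to an unadjusted difference although the stated test uses change. All of this lowers the weight of the point. It does not remove it: eligibility wording and what is captured at enrolment belong in the protocol, and section 7.1 itself names a paired test while powering a between-group difference.

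**Conclusion.** The point holds in a limited form. The eligibility and allocation rules create a mixed control group, section 5.3 describes it differently, and the visible text does not provide for telling the two kinds of control apart. The powered comparison is harder to interpret as a result, but section 7.1's arithmetic is sound and is not contradicted.

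The size and direction of any bias on PHQ-ADS are unknown. The 0.6 to 1.2 points (unadjusted) and 0.5 to 1.25 points (different course) rest on an assumed 25% share and assumed gaps. If few people enter by a medical route, both the bias and the power cost of setting them aside are small, and only recording the route will show that. Neither control subset matches Group A, so no choice between them makes the comparison causal.

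**What to change.** 1. **Sections 5.3 and 5.4.** Define Group B in 5.3 by all three routes given in 5.3.2 (declined, failed screen, physician judgement), and add the physician route to the allocation sentence in 5.4.
2. **Section 5.4.** State that the route of entry to Group B (choice, failed screen, physician) is recorded at enrolment.
3. **Section 7.1, main analysis.** State that follow-up PHQ-ADS is compared between Group A and all of Group B, adjusted for baseline PHQ-ADS. Limit the signed-rank test to change within each group, and amend Table 1 to agree.
4. **Section 7.1, sensitivity analysis.** Repeat the comparison with Group B members who entered by choice, and note its lower power.
5. **Limitation.** State that decliners differ from Group A on interest and are unscreened, that screen failures differ on fitness, and that causal claims are limited accordingly.

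The cost is one enrolment field and a few sentences. Baseline PHQ-ADS is already collected from both groups. The main analysis loses no participants and should gain precision from baseline adjustment. Only the sensitivity analysis loses power. No extra recruitment is needed for it. Keeping 36 evaluable by-choice controls at an assumed 75% share would take 36/(0.75 × 0.90) = 53.3, so 54 people in Group B instead of 40, which a sensitivity analysis does not justify.
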